#### **6.5. PHARMACOKINETICS ANALYSIS SET (PKAS)**

The PKAS is defined as all patients who received at least 1 dose of HMPL-523 and have at least 1 PK sample obtained and analyzed.

### **7. GENERAL CONSIDERATIONS**

#### **7.1. REFERENCE START DATE AND STUDY DAY**

Study Day will be calculated from the reference start date and will be used to show start/stop day of assessments and events.

Reference start date is defined as the day of first administration of treatment and will appear in every listing where an assessment date or event date appears.

If the date of the event is on or after the reference date, then:

- Study Day = (date of event – reference date) + 1.

If the date of the event is prior to the reference date, then:

- Study Day = (date of event – reference date).

In the situation where the event date is partial or missing, the date will appear partial or missing in the listings. Study day, and any corresponding durations, will be presented based on the imputations specified in [section 7.8: Handling of Missing Data](#).

#### **7.2. BASELINE AND CHANGE FROM BASELINE**

Unless otherwise specified, baseline is defined as the last non-missing measurement taken prior to the day of first administration of treatment (including unscheduled assessments). Bone marrow biopsy and/or aspirate were done at baseline or up to 3 months before of the Cycle 1 Day 1. In the case where the last non-missing measurement is taken on the day of first administration of treatment without time point collected, that measurement will be considered baseline. For

HMPL-523

Electrocardiogram (ECG) parameters, last assessment performed prior to or on first dose date with time point marked as “pre-dose” will be considered as baseline. For those patients without pre-dose ECG record at date of the first dose, the last non-missing measurement taken prior to the day of first administration of treatment will be treated as baseline. Adverse Events (AEs) and medications commencing on the day of first administration of treatment will be considered post-baseline.

For quantitative measurements, change from baseline (CFB) will be calculated as:

- $CFB = \text{Assessment value at each visit} - \text{Baseline value}$ .

Percentage CFB (% CFB) will be calculated as:

- $\% CFB = (\text{Assessment value at each visit} - \text{Baseline value}) / \text{Baseline value} \times 100$ .

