5.6 Study Assessments

5.6.1 Definitions of Study Assessments

All patients will be closely monitored for safety and tolerability throughout the study. Continuous dosing with HMPL-523 will be offered to patients until disease progression, death, intolerable toxicity, at investigator's discretion that the patient can no longer benefit from the study treatment, patient withdrawal from the study, or the end of study.

The schedule of assessments is provided in [Appendix 1](#), and the schedule of PK sample collection is provided in [Appendix 2](#) and [Appendix 3](#). Unless otherwise indicated, the visit window during the treatment period is ± 3 days (± 1 day during the DLT observation window). Except for the electrocardiogram (ECG), echocardiogram/multigated acquisition scan (MUGA), bone marrow biopsy, and/or aspirate and tumor assessment, all the assessments should be performed before dosing if the study drug is to be taken on the visit day. Unscheduled assessments can be performed if there is a clinical indication.

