5.6.7 Vital Signs

Vital signs will be collected at screening; Days 1, 8, 15, and 22 of Cycle 1; Days 1 and 15 of Cycle 2; Day 1 of every cycle from Cycle 3 onwards; and at study completion or early termination. Vital signs include measurements of body temperature (axillary, oral, or tympanic), heart rate, respiratory rate, and systolic and diastolic blood pressures while the patient is in a seated position. The patient should be seated for 5 minutes before the measurement of blood pressure.

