### **7.3. ON TREATMENT PERIOD AND WORST POST-BASELINE**

For the analysis purpose, on treatment period is defined as the period from the day of first dose of treatment to 37 days after the last dose of treatment or the initiation of new antineoplastic therapy, whichever comes earlier.

The severity of adverse events and laboratory results depends on CTCAE grade. The worst post baseline value is defined as the highest CTCAE grade during on treatment period.

The worst post-baseline abnormality is defined in the order of Abnormal, Clinically Significant>Abnormal, Not Clinically Significant>Normal during the on-treatment period.

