### 17.4. LABORATORY EVALUATIONS

The following laboratory evaluations will be summarized in tables:

- Chemistry
- Coagulation
- Fasting lipid profile
- Hematology
- Leukocyte immunophenotyping
- Serum immunoglobulin
- Serum amylase and lipase
- Serum  $\beta$ -2 microglobulin
- Urinalysis

The following laboratory evaluations will be listed in listings:

- Chemistry
- Coagulation
- Fasting lipid profile

HMPL-523

- 
- Hematology
  - Leukocyte immunophenotyping
  - Serum immunoglobulin
  - Serum amylase and lipase
  - Serum  $\beta$ -2 microglobulin
  - Urinalysis
  - Pregnancy test
  - Viral serology

Quantitative laboratory measurements reported as “< X”, i.e. below the lower limit of quantification (LLQ), or “> X”, i.e. above the upper limit of quantification (ULQ), will be converted to X for the purpose of quantitative summaries, but will be presented as recorded, i.e. as “< X” or “> X” in the listings.

Descriptive statistics for all quantitative laboratory evaluations and change from the baseline will be presented in SI units for each visit.

For laboratory parameters graded by NCI CTCAE, version 5.0 (see [Appendix 2](#)), changes in CTC grade laboratory data will be summarized as shift table from baseline to worst post-baseline grade. Baseline CTCAE grade is derived from the last laboratory assessment prior to the first administration of study medication, as defined in [section 7.2](#). Worst (maximum) post-baseline CTCAE grade is derived with all measurements from the first dose administration of study medication to no more than 37 days after the last dose of study medication or new anti-cancer therapies, which comes earlier. Otherwise, the shift table will be presented by ‘normal’, ‘abnormal but not clinically significant’, ‘abnormal and clinically significant’.

All CTCAE Grade 1 or higher abnormalities in laboratory tests will be flagged in the listings.

The incidence of patients with the following abnormal liver function tests (Hy’s Law) at any time post baseline will also be summarized:

HMPL-523

- ALT or AST  $\geq 3$  x ULN and  $\leq 5$  x ULN
- ALT or AST  $\geq 5$  x ULN
- Total bilirubin  $\geq 2$  x ULN
- (ALT or AST  $\geq 3$  x ULN) and total bilirubin  $\geq 2$  x ULN
- (AST or ALT  $\geq 3$  x ULN) and total bilirubin  $\geq 2$  x ULN and ALP  $< 2$  x ULN

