### **17.9. ECOG PERFORMANCE STATUS**

The incidence of ECOG performance status will be presented by visit. In addition, ECOG performance status will be presented using shift table to compare baseline to the worst post-baseline value. Values from post-baseline unscheduled visit will be considered when deriving worst post-baseline value.

All ECOG data will be listed.

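### SAP 7.2 bars a timed Day 1 pre-dose value (other than ECG) from being baseline but accepts an untimed one, and SAP 7.3 counts all of Day 1 as on treatment

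*SAP*

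**What the plan says.** **Baseline.** In SAP 7.2, "baseline is defined as the last non-missing measurement taken prior to the day of first administration of treatment", unscheduled assessments included. Two exceptions follow. The first covers a last non-missing value on Day 1 that has no time point: where the "measurement is taken on the day of first administration of treatment without time point collected, that measurement will be considered baseline". The second covers ECGs, for which baseline is the "last assessment performed prior to or on first dose date with time point marked as" pre-dose, or an earlier day's record if there is none.

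**On-treatment period.** In SAP 7.3, "on treatment period is defined as the period from the day of first dose of treatment". Nothing is carved out for values taken that day before the dose.

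**Timing of visits.** Protocol 5.6.1 exempts ECG, echocardiogram/MUGA, bone marrow and tumor assessment; otherwise "all the assessments should be performed before dosing if the study drug is to be taken on the visit day". Protocol 5.6.7 states: "Vital signs will be collected at screening; Days 1, 8, 15, and 22 of Cycle 1". Protocol 5.6.5 and 5.6.8 likewise place ECOG and the physical examination, which includes weight, at screening and on Day 1.

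**Use of baseline.** SAP 17.6 reports change from baseline by visit for vital signs and weight. In SAP 17.9, "ECOG performance status will be presented using shift table to compare baseline to the worst post-baseline value". For laboratory data SAP 17.4 says: "Baseline CTCAE grade is derived from the last laboratory assessment prior to the first administration of study medication", and it cites section 7.2.

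**The concern.** The natural baseline is the last value before the first dose. For vital signs, weight and ECOG, the protocol schedules such a value on Day 1. The SAP cuts at the calendar day instead, and its exception admits the value with less documentation while leaving out one that can be shown to be pre-dose. The ECG sentence shows that the authors regard a Day 1 pre-dose record as a proper baseline, but that treatment was not extended to other measurements.

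At stake is attribution in the safety tables. With no control arm, a change between screening and Day 1 that is tabulated as change on treatment has nothing to offset it. There is also a reproducibility problem: two programmers could derive different baselines and different worst post-baseline values from the same text.

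**Working it through.** The plan gives no figure to reproduce. The check applies SAP 7.2 and 7.3 to each kind of Day 1 record.

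**Inputs.** Screening runs from D-21 to D-1 (Protocol Appendix 1). Vital signs, ECOG and weight are scheduled on Cycle 1 Day 1, before dosing. The visit-window table in SAP 7.6 gives ECOG and vital signs their own Day 1 window.

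**Case 1: Day 1 pre-dose value with a time point, not ECG.** The general rule excludes it because it is not before the day of first dose. The untimed exception does not apply, and neither does the ECG exception. Baseline is the last earlier value, normally screening, so up to 21 days old. The Day 1 value falls in the on-treatment period. For any later visit,

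change from baseline = (visit value − Day 1 value) + (Day 1 value − screening value).

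The second term arose before any drug was taken. It appears alone in the Day 1 row and is carried into every later row. For ECOG, a hypothetical patient with 0 at screening, 1 on Day 1 before dosing and 1 thereafter is tabulated as 0 to 1. A pre-dose baseline would give 1 to 1.

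**Case 2: Day 1 value without a time point, not ECG.** The exception makes it baseline. It still lies within the on-treatment period of 7.3, so the sections overlap. In the by-visit tables the Day 1 change is then Day 1 value − Day 1 value = 0 by construction. If 7.3 also governs the ECOG shift table, then

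worst post-baseline = max(Day 1 value, later values) ≥ Day 1 value = baseline.

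On that reading no improvement could be shown, and a patient with no later assessment would appear as unchanged. A hypothetical patient with 1 on Day 1 and 0 thereafter is classed as 1 to 1; leaving out the baseline value gives 1 to 0.

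**Case 3: Day 1 ECG marked pre-dose.** It is baseline under its own rule. There is no problem here, and the QTcF change categories in SAP 17.5.1 are sound on this point.

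**Case 4: routine laboratory tests.** Hematology, chemistry, and amylase/lipase are not scheduled on Cycle 1 Day 1 (Protocol 5.6.9 and Appendix 1). The 17.4 wording (before the first administration) and the 7.2 wording (before the day of it) can part only for an unscheduled Day 1 sample. Such a hematology sample could be baseline under 17.4, yet the window table's range of 1 to 11 would map it to the Day 8 visit.

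**Mixed recording.** If time points exist for some patients only, one table would combine Case 1 and Case 2 baselines.

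**The case against.** The strongest reply is that no section shows a time point being collected for vital signs, weight or ECOG. The protocol schedules them by day only; pre- and post-dose time points are specified for ECGs and PK samples. In the ECG sentence of SAP 7.2, a time point is a nominal label. Read that way, the untimed exception may have been written for exactly these assessments, and it makes Day 1 the baseline. This stands. A reader might infer that baseline reverts to screening for everyone, but the documents support that only where a time point exists.

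It can also be said that 7.3 defines worst post-baseline for CTCAE grades and for normal/abnormal categories, that ECOG is neither, and that a value used as baseline is not ordinarily also post-baseline. This too is fair. The ECOG consequence in Case 2 depends on carrying 7.3 over to 17.9. The overlap remains on the page all the same, since no sentence removes the baseline value from the on-treatment period.

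A reader might also want a patient count. If 10% of the 48 expansion patients moved from ECOG 0 to 1 between screening and Day 1, 0.10 × 48 = 4.8 would appear as on-treatment worsening. The documents do not support that figure. The 10% is assumed, every Day 1 ECOG would have to be timed, and the 48 leaves out the escalation stage. With the proportion timed anywhere from 0 to 1 and the rate from 0 to 10%, the range is 0 to 4.8.

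Finally, the apparent conflict between 17.4 and 7.2 is close to empty, because 17.4 defers to 7.2 and routine bloods are not due on Day 1.

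**Conclusion.** The drafting fault is real and minor. As written, SAP 7.2 gives the wrong baseline for a timed, non-ECG, pre-dose Day 1 value. For an untimed one, 7.2 and 7.3 together let a single value be both baseline and on treatment. Which branch applies depends on whether time points are recorded for vital signs, weight and ECOG, and the documents do not say. The number of patients affected therefore cannot be derived and may be zero.

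The effect stays within descriptive tables: change from baseline for vital signs and weight (17.6), the ECOG shift table (17.9), and the baseline weight, BMI and ECOG entries in SAP section 10 that use the same definition. DLTs, TEAE classification, ORR and PFS do not depend on it, and no sample-size figure changes.

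**What to change.** - **SAP 7.2:** for measurements other than ECG, define baseline as the last non-missing value before the first dose by date and time. Where no time is recorded, treat Day 1 assessments that Protocol 5.6.1 requires before dosing as pre-dose.
- **ECG:** keep the present rule (a record marked pre-dose, otherwise an earlier day). ECGs are exempt from the before-dosing requirement and are also taken 4 hours post-dose on Day 1, so an unlabelled Day 1 ECG must not be presumed pre-dose.
- **SAP 7.3:** state that post-baseline measurements are those after the first dose, and that the value used as baseline is excluded.
- **SAP 17.4 and the visit-window table in 7.6:** align the wording and the Day 1 entries with the above.

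The cost is a short edit in each of these places, with no new data. SAP section 2 allows revision up to final database lock; after that, the handling used should be documented in the clinical study report.

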### **7.3. ON TREATMENT PERIOD AND WORST POST-BASELINE**

For the analysis purpose, on treatment period is defined as the period from the day of first dose of treatment to 37 days after the last dose of treatment or the initiation of new antineoplastic therapy, whichever comes earlier.

The severity of adverse events and laboratory results depends on CTCAE grade. The worst post baseline value is defined as the highest CTCAE grade during on treatment period.

The worst post-baseline abnormality is defined in the order of Abnormal, Clinically Significant>Abnormal, Not Clinically Significant>Normal during the on-treatment period.

### **7.4. RETESTS, UNSCHEDULED VISITS AND EARLY TERMINATION DATA**

In general, for by-visit summaries, data recorded at the nominal visit will be presented. Unscheduled measurements will not be included in by-visit summaries but will contribute to the best/ worst case value where required (e.g. shift table).

In the case of a retest (visit-specific unscheduled visit number assigned), the latest non-missing measurement among all scheduled and unscheduled measurements for that visit will be used for by-visit summaries.

For ECG triplicate records, the mean value will be used for by visit summaries.

Early termination data of patients prematurely discontinued from study medication will be presented together with the end of treatment assessment for study medication completers.

Listings will include scheduled, unscheduled, retest and early discontinuation data.

HMPL-523

## 7.5. SUBGROUPS

Not applicable.

## 7.6. WINDOWING CONVENTIONS

It is expected that there will be a variation between patients in the actual number of study days from the start of administration of study drug within each cycle defined as Day 1, to the dates that the scheduled visits occurred. To handle this, for tables and figures where data are grouped by visit, assessments will be categorized using visit windows based on study days (relative to the Day 1 of each cycle). The visit-window mapping is described in **Error! Reference source not found.** Visit-based summaries will be based on the windowed visits. All data, whether or not within the visit windows, will be presented in patient's listings. For windowed visits during the treatment cycles, if more than one visit occurs during a visit window, the visit closest to the scheduled day will be assigned to the windowed visit. If two visits are equidistant from the scheduled day, the later visit will be assigned to the windowed visit. If there are multiple assessments on the same day, the worst case will be used.

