5.6.10 Electrocardiogram

All ECGs are required to be performed using a 12-lead tracing. Electrocardiogram measurements will include PR interval, QRS interval, RR interval, QT/QTcF interval, and heart rate.

Triplicate ECGs, approximately 2 minutes apart, should be performed at screening and pre-dose and at 4 hours \pm 15 minutes post dose on Days 1 and 15 of Cycle 1 in order to evaluate concentration-QT relationship for HMPL-523. Single ECGs will be conducted at any time on Day 1 of Cycle 2. From Cycle 3 onwards, ECGs will be performed as clinically indicated.

Electrocardiograms will be reviewed by the investigator to determine patient eligibility at screening. Additional ECGs and other cardiac monitoring will be provided as clinically indicated during the study.

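### SAP 7.4 and 7.6 set contradictory rules for the same by-visit safety tables, and 7.6 merges the pre-dose and 4-hour ECGs on Cycle 1 Days 1 and 15 by a worst-case rule

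*SAP*

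**What the plan says.** SAP 7.4 (Retests, Unscheduled Visits and Early Termination Data) sets four rules for by-visit summaries:

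- Visit basis: "In general, for by-visit summaries, data recorded at the nominal visit will be presented".
- Unscheduled values: "Unscheduled measurements will not be included in by-visit summaries but will contribute to the best/ worst case value where required".
- Retests: "the latest non-missing measurement among all scheduled and unscheduled measurements for that visit will be used for by-visit summaries".
- ECGs: "For ECG triplicate records, the mean value will be used for by visit summaries".

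SAP 7.6 (Windowing Conventions) covers tables and figures grouped by visit and sets three rules:

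- Visit basis: "Visit-based summaries will be based on the windowed visits".
- Several visits in a window: "if more than one visit occurs during a visit window, the visit closest to the scheduled day will be assigned to the windowed visit", with the later visit taken in a tie.
- Several assessments on a day: "If there are multiple assessments on the same day, the worst case will be used".

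Section 7.6 makes no exception for retests, unscheduled values or triplicates, and neither section refers to the other.

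Protocol 5.6.10 says that triplicate ECGs "should be performed at screening and pre-dose and at 4 hours" after dosing on Days 1 and 15 of Cycle 1. The window table in SAP 7.6 gives the ECG only two Cycle 1 windows: Days 1 to 2, and Day 3 to three days before the end of the cycle.

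**The concern.** Both sections govern the same outputs: the by-visit laboratory, vital-sign and ECG summaries and the by-visit ECG threshold categories in SAP 17.4 to 17.6. Two programmers who each follow the SAP could produce different tables, and nothing in the text would show which is right.

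The rules also differ in kind. Taking the value closest to schedule, or the latest retest, does not look at the result. Taking the worst does, so it pushes a table of means in one direction. For laboratory values and vital signs, same-day repeats would arise only by chance. For ECGs they are planned, at two time points that the protocol sets apart so that the concentration-QT relationship can be examined.

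**Working it through.** The plan states no figure on this point, so there is none to reproduce. The check has two parts.

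**1. Both rule sets applied to the same records.** These are hypothetical ALT values for Cycle 1 Day 8 (scheduled day 8; chemistry window Days 1 to 11 in the 7.6 table).

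| Records | 7.4 | 7.6 |
|---|---|---|
| Scheduled Day 7 = 120; retest Day 10 = 40 | 40 (latest retest) | 120 (1 day from schedule against 2) |
| Scheduled Day 8 = 120; retest on the same day = 40 | 40 (latest retest) | 120 (same-day worst) |
| Scheduled Day 9 = 40; unscheduled Day 8 = 120 | 40 (unscheduled value left out) | 120 (closest to schedule) |

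The third row assumes that an unscheduled visit can fill a window under 7.6. That section does not exclude it.

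**2. ECGs, with triplicates first averaged within each time point as 7.4 requires.**

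Inputs:
- Three tracings per time point and two time points per day (Protocol 5.6.10), so two triplicate means on one day in one window.
- Between-tracing SD of QTcF, written s. The documents give none; 5 to 10 ms is assumed.
- Independent readings, no drug effect, and worst taken as highest.

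Steps:
- SD of a triplicate mean = s/√3 = 0.577 s.
- Expected maximum of two independent standard normal values = 0.5642.
- Expected excess of the worse mean over the average of the two = 0.5642 × s/√3 = 0.326 s, or about 0.33 s.
- For s = 5 ms: 0.326 × 5 = 1.6 ms. For s = 10 ms: 0.326 × 10 = 3.3 ms.

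By symmetry, with no drug effect about half of the patients would contribute a pre-dose value to the row and half a 4-hour value, so the row describes neither time point.

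**Laboratory values for comparison.** The Schedule of Activities plans no same-day replicates. If 5% to 25% of patients happened to have one same-day duplicate (assumed), the visit mean would shift by 0.05 × 0.5642 = 0.03 to 0.25 × 0.5642 = 0.14 within-patient SD.

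**The case against.** The best defence is that 7.4 opens with a general qualifier and then gives a specific rule for the only planned replicates. On that reading triplicates are averaged first, and the same-day rule in 7.6 acts on what is left. This stands, and it limits the size of the problem. A reader might apply 7.6 to the raw tracings and infer a false QTcF rise of 0.85 SD (worst of 3; 4.2 to 8.5 ms for an SD of 5 to 10 ms) or 1.27 SD (worst of 6; 6.3 to 12.7 ms). Both figures require ignoring the triplicate-mean rule in 7.4, so the documents do not support them.

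A second defence is that SAP 7.2 picks the baseline ECG by its pre-dose label, so time point is recorded, and on Day 1 of Cycle 1 the pre-dose set is the baseline. That is correct, and it makes Day 15 the clearer case. But 7.6 does not remove the pre-dose set from the Day 1 window. If it stays in, the Day 1 value is the worse of baseline and the 4-hour mean, and change from an averaged pre-dose baseline cannot be negative.

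A third is that selection might cancel in change from baseline. It would if baseline were chosen the same way, but 7.2 takes the last pre-dose assessment, not the worst.

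Fourth, a reader might infer a general adverse bias in laboratory values and vital signs. That does not follow. No same-day repeats are planned for them, and SAP 7.3 defines worst only by CTCAE grade and by normal or abnormal category. An ungraded vital sign therefore has no stated direction in which to be biased.

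**Conclusion.** The contradiction between 7.4 and 7.6 is real. It covers visit basis, unscheduled values, and retest against closest or same-day worst, and it changes reported values in simple examples. This is a conflict between stated rules, not missing detail.

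For ECGs on Cycle 1 Days 1 and 15, a distinct problem remains after triplicate averaging: two time points share a window and a day, and the only rule left is worst case. The expected distortion is about 0.33 of the between-tracing SD, or about 1.6 to 3.3 ms. This rests on an assumed SD of 5 to 10 ms, independent readings and no drug effect. It reaches the by-visit QTcF means and changes (SAP 17.5) and the by-visit threshold categories (SAP 17.5.1).

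A reader might go on to doubt the main results. The documents give no ground for that: DLTs, adverse-event incidence, best overall response, response rate, PFS and the worst-post-baseline shift tables follow other rules. Nor is a by-visit mean table itself the concentration-QT analysis, and all ECG data are listed. The correction should be made, but it concerns descriptive safety tables only.

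**What to change.** Replace the conflicting text in 7.4 and 7.6 with one hierarchy:

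1. By-visit tables use windowed visits and take the scheduled value closest to the scheduled day.
2. Unscheduled values do not enter by-visit tables, except that a visit-specific retest replaces the value it repeats, using the latest non-missing result.
3. ECG triplicates are averaged within each time point, and pre-dose and 4-hour values are summarised, and categorised against the thresholds, as separate time points.
4. Worst case is confined to shift and worst-post-baseline outputs, with the direction stated for each parameter.

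Under this hierarchy all three ALT examples give 40. Deleting only the nominal-visit sentence from 7.4 would not be enough, because the retest and unscheduled-value conflicts would remain.

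No new data are needed, and SAP section 2 allows revision before the final database lock. The cost is the wording and minor reprogramming. SAP section 5 records a soft lock and a preliminary evaluation that included selected safety endpoints, so some by-visit figures may differ slightly from those outputs. Any difference should be explained in the study report.
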